- **Methods, Research Plan, and Design**

- **Study design**

This study will be a prospective 2-year randomized, open label, clinical trial, using daily dose sublingual versus twice daily dose sublingual versus transdermal 17-beta estradiol in transgender female patients. Primary outcome is degree of testosterone suppression. Secondary outcome to measure safety and tolerability will

include liver enzymes, thrombogenic, and metabolic factors. Patients will be evaluated every 6 months during the length of the study

b. Subjects

Inclusion criteria: Female transgender patients between the ages of 18 to 45 years of age who are seen at the Washington University Transgender Center. Patients must have met the eligibility and readiness criteria for gender-affirming hormone therapy.

Exclusion criteria: Use of GnRH agonist for the last 12 months, history of liver disease, dyslipidemia requiring treatment, drug use, alcohol use (>2drinks per day), cigarette smoking, history of blood clot (venous thromboembolism, pulmonary embolism), history of hyperkalemia, history of Addison's disease, concomitant use of eplerenone.

Patients who have been referred to the Washington University Transgender Center for feminizing hormonal therapy and meet the inclusion criteria, will undergo consent process before initial evaluation. Methods for recruitment includes phone calls, emails, letters, and EPIC slicer dicer. For consent, physical or electronic consent form will be provided.

If consent is obtained, patients will be assigned to either daily sublingual vs twice daily sublingual vs transdermal 17-beta estradiol. Assignment will be done through block randomization.. Using the inclusion criteria, our center provides care to 150-200 new transgender female patients in a year for initiation of female hormone therapy.

We aim to enroll a total of 70 patients. This is a pilot study, which results will guide the feasibility, design, and implementation of a larger clinical trial. To account for 15% of potential dropout, we have planned to enroll a total of 80 patients.

- Research Plan**

The proposed clinical trial involves 2 research aims to be conducted over two years (Table 1). Subjects will be recruited from the Washington University Transgender Center. The Center is projected to see more than 1,000 patients every year, of which 150-200 are new transgender female patients for initiation of FHT.

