Patients who agree to participate in the study and meet inclusion criteria will undergo the evaluation described in Table 2. Data of interest will be collected on all patients enrolled and will be saved on a database created in Research Electronic Data Capture (REDCap). Information to be collected will include:

1. Demographic and anthropometric variables: Parameters will be routinely collected through chart review.
2. Laboratory testing: During each visit, we will obtain hormone levels, coagulation factors, metabolic factors, electrolytes level. A hematologist will review the lab results and communicate any recommended interventions (including stopping medication) to the participant's treatment team.

Initial evaluation will include patient history, physical examination, and baseline labs. During the initial visit, patients will be started on spironolactone and 17-beta estradiol transdermal or or daily sublingual or twice daily sublingual based on their treatment group assignment. Our team will check hormonal levels every 4 weeks (+/- 2 weeks) until estradiol level is within goal (see dosing guidelines) as established by standard of care. Once patients are started on estradiol, they will be asked to attend 6 more visits for the 2 years duration of the study as described in table 2.

Dosing guidelines:

Per the current standard of treatment, all study medications are initiated at the lowest available clinical dose and titrated to effectiveness at the study clinician's discretion by 6 months of study participation, using plasma total testosterone level in the cisgender female range (<50ng/dL) with serum estradiol level that should not excess the peak physiologic range 100-200 pg/mL. In some cases, medication doses will be titrated at monthly study follow up visits to optimize treatment response.

Spironolactone:

Starting dose will be 50 mg daily

Plan to increase 50 mg monthly to standard dose of 200 mg daily

For patients randomized to transdermal (patch) estradiol:

Starting dose will be 100 mcg/24hrs

Plan to increase by 100 mcg/24hrs every month

Max dose 400 mcg/24hrs

Goal is to achieve a serum estradiol level between 100-200 pg/mL and to suppress testosterone to cisgender female levels

Estradiol levels will be measured in the morning (fasting sample)

For patients randomized to daily sublingual estradiol:

Starting dose will be 2 mg daily

Plan to increase every month by 2 mg daily

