Goal is to achieve serum estradiol level between 100-200 pg/mL and to suppress testosterone to cisgender female levels.

Estradiol levels will be measured in the morning (fasting sample).

For patients randomized to twice daily dose sublingual estradiol

Starting dose will be 1 mg twice daily

Plan to increase every month by 2 mg daily

Goal is to achieve serum estradiol level between 100-200 pg/mL and to suppress testosterone to cisgender female levels

Estradiol levels will be measured in the morning (fasting sample).

Table 1. Planned Research Timeline

Data cleaning and analysis										•	•	•	•
Grant application				•	•	•	•						
Final results manuscript										•	•	•	
Presentation preparation										•	•	•	

Table 2. Description of the evaluation and laboratory testing in each visit during the clinical trial

Study visit	Baseline	6 months +/- 2 months	12 months +/- 2 months	18 months +/- 2 months	24 months +/- 2 months
Anthropometric measurement	•	•	•	•	•
Metabolic factors	•	•	•	•	•
Hormone levels	•	•	•	•	•
Electrolytes	•	•	•	•	•
Liver function test	•	•	•	•	•
Coagulation factors	•	•	•	•	•
Lipid Panel	•		•		•

- Benefit/Risk assessment**

i. Benefits

Direct benefits from this study to participants are anticipated. During the research study, their tolerability and side effects will be monitored closely so any changes can be detected earlier. Also, participants may feel gratified by contributing to the field. Patients will have the opportunity to help us improve services and treatment options for them and future generations.

ii. Risks

Potential risks with this study are no different than the risks that may occur while receiving gender affirming therapy. This may include changes in their lipoprotein profile and triglycerides level (14) and increase risk of venous thromboembolism, diabetes, high blood pressure, coronary heart disease, hepatotoxicity. While the patient is receiving gender affirming therapy, the investigators will provide careful attention to laboratory results.

Laboratory testing will be obtained every 3 months for the first year, and every 6 months on the second year. For this purpose, placement of an intravenous (IV) access may be required. IV access or venipuncture may be associated with possible minor discomfort or pain when inserted.

- Statistical methods and Data Analysis**

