Baseline characteristics and laboratory results will be reported as mean \pm SD, median (interquartile range), or percentages. Independent T-test will be used to analyze the difference between treatment groups. We may use Wilcoxon rank sum test in case of non-normal distribution.

g. Limitations and contingent plans

A potential limitation to this study is the difficulty of recruitment since the PI is a First Year Clinical Fellow with a heavy clinical rotation. Our project is also supported by the director of the Washington University Transgender Center which will improve the recruitment of patients. Also, the co-directors of the Washington University Transgender Center at St Louis Children's Hospital are supporting the project, therefore, we could increase our enrollment numbers by recruitment patients seen in their clinic. Another limitation is the cost of the entire panel of thrombogenic factors. We could address this by just testing the most valuable test (thrombin) which has been used in previous research to assess the thrombotic risk in postmenopausal women on hormone replacement therapy.

- **References**

- Unger CA. Hormone therapy for transgender patients. *Transl Androl Urol.* 2016;5(6):877-884. doi:10.21037/tau.2016.09.04
- American Psychiatric Association. Diagnostic and Statistical Manual of Mental Disorders. 5th ed. Washington, DC: American Psychiatric Press; 2013
- Unger CA. Hormone therapy for transgender patients. *Transl Androl Urol.* 2016;5(6):877-884. doi:10.21037/tau.2016.09.04
- Unger CA. Hormone therapy for transgender patients. *Transl Androl Urol.* 2016;5(6):877-884. doi:10.21037/tau.2016.09.04

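### The only between-group tests are unadjusted, although testosterone is also measured at baseline; baseline adjustment would cost about 2% of variance on average if uninformative and may gain precision

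*Combined protocol and SAP*

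**What the plan says.** The Study design section states: "Primary outcome is degree of testosterone suppression". Aim 1 says that this is assessed from total testosterone over two years. No scale is given (level, change from baseline, visit average or proportion suppressed), and no primary visit.

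The Statistical methods and Data Analysis section has three sentences. The first covers descriptive summaries. The second is "Independent T-test will be used to analyze the difference between treatment groups". The third is "We may use Wilcoxon rank sum test in case of non-normal distribution"; it gives a condition for switching but not how the condition will be judged. No baseline term, change score or repeated-measures model appears anywhere.

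The follow-up data are already planned. Table 2 marks hormone levels at baseline and at 6, 12, 18 and 24 months, which agrees with the Study design section: "Patients will be evaluated every 6 months during the length of the study". Two other places imply more visits. The Research Plan says of patients who have started estradiol that "they will be asked to attend 6 more visits for the 2 years duration of the study as described in table 2", and the Risks section says "Laboratory testing will be obtained every 3 months for the first year, and every 6 months on the second year". The last gives months 3, 6, 9, 12, 18 and 24, which is six visits against Table 2's four. Months 6, 12, 18 and 24 are common to both, and baseline is measured under either.

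The Dosing guidelines set a common titration target for every arm, to be reached by 6 months: "using plasma total testosterone level in the cisgender female range (<50ng/dL").

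**The concern.** A t-test implies a continuous outcome. If that outcome is the follow-up level or a per-patient average over visits, the test ignores a baseline value of the same measure that every patient has provided. If it is change from baseline, the test uses baseline but fixes its slope at 1 instead of estimating it. In either case an analysis of covariance (ANCOVA) could give a tighter estimate from the same samples.

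Precision matters here because the groups are small: about 23 evaluable patients per arm. The pilot is also meant to guide a larger trial, and the baseline to follow-up correlation is itself an input for sizing that trial.

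**Working it through.** **Inputs from the documents.** Three arms; target 70; 15% dropout; 80 to be enrolled.

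**Assumptions.** Equal allocation; two-sided 95% intervals; normally distributed values; and a range for r, the correlation between baseline and follow-up testosterone. The documents give no SD, correlation, alpha or power.

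**The plan's own figure.** 70 × 1.15 = 80.5, which matches the stated 80 within rounding (70/0.85 = 82.4 would not). With 15% lost from 80, 80 × 0.85 = 68 remain, or 22.7 per arm. I use 23 per arm: N = 69 for three arms, N = 46 for two.

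**Step 1: follow-up level at one visit.** With g arms in the model, the expected variance of an ANCOVA contrast relative to the unadjusted one is (1 − r²) × [1 + 1/(N − g − 2)]. The bracket is 1 + 1/64 = 1.016 for three arms and 1 + 1/42 = 1.024 for two.

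| Assumed r | Three-arm model | Two-arm model |
|---|---|---|
| 0 | 1.016 | 1.024 |
| 0.1 | 1.005 | 1.014 |
| 0.2 | 0.975 | 0.983 |
| 0.3 | 0.924 | 0.932 |
| 0.5 | 0.762 | 0.768 |

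Break-even is r = √(1 − 1/1.0156) = 0.124 for three arms and √(1 − 1/1.0238) = 0.152 for two. Counting the lost degree of freedom moves these to about 0.126 and 0.157.

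**Step 2: the cost in a single data set.** The r = 0 figures are averages over randomisations. Simulating chance baseline imbalance at r = 0 gives a mean variance inflation of 1.016 and a 95th percentile of about 1.06 with three arms. With two arms these are 1.024 and about 1.09.

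**Step 3: interval width.** With the SD pooled over three arms and no baseline term, the 95% half-width is t(66) × √(2/23) = 0.589 SD. With baseline it is t(65) × √(2/23 × (1 − r²) × 1.0156), which gives 0.594, 0.591, 0.582, 0.566 and 0.514 SD at r = 0, 0.1, 0.2, 0.3 and 0.5. The two-arm t-test gives t(44) × √(2/23) = 0.594 SD; its excess over 0.589 comes from not pooling the third arm and has nothing to do with baseline.

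**Step 4: change from baseline.** Let s = SD(baseline)/SD(follow-up). The variance of the t-test on change relative to ANCOVA is (1 + s² − 2rs)/(1 − r²), before ANCOVA's 1/64 cost. Its minimum is 1, at s = r. At r = 0.3 it is 0.95/0.91 = 1.04, 1.40/0.91 = 1.54 and 3.80/0.91 = 4.18 for s = 0.5, 1 and 2. Dividing by 1.0156 to include the cost gives 1.03, 1.51 and 4.11.

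**Step 5: visit average.** With correlation ρ between follow-up visits, the average of four visits correlates with baseline at r/√((1 + 3ρ)/4). Putting this in the Step 1 formula for three arms, with ρ from 0.5 to 0.8, gives factors of 0.95 to 0.97 at r = 0.2 and 0.87 to 0.91 at r = 0.3.

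**Step 6: the price of one common variance.** A three-arm model with a single residual variance lets the third arm's spread enter a contrast between the other two. If the third arm's SD is half the others', the pooled variance is (1 + 1 + 0.25)/3 = 0.75 of the correct value, and simulated coverage of the nominal 95% interval is 91%. If it is double, the pooled variance is (1 + 1 + 4)/3 = 2 times the correct value and the interval is about 40% wider than the two-arm one. The two-arm t-test keeps 95% coverage in both cases.

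**The case against.** The strongest case against is that no error has been shown. Randomisation makes the t-test valid, and a reader who inferred bias or an invalid analysis from the missing baseline term would be wrong. This stands.

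Nor is the gain assured. All arms are titrated toward the same testosterone range by 6 months, and every Table 2 follow-up falls at about that point or later, so r may be low. At r = 0 or 0.1 adjustment is slightly worse, and at r = 0.2 the half-width shrinks by only 1.2% (0.589 to 0.582). A reader might take the 24% reduction at r = 0.5 as what the plan forfeits; the documents give no correlation to support that or any other figure.

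A reader might also take 2% as a ceiling on the cost. It is an average at r = 0, and Step 2 shows larger losses in some data sets. Adjustment in a three-arm model with one common variance also carries the separate risk in Step 6, and nothing in the documents supports equal variances across arms. The fix therefore avoids that assumption.

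Finally, the undefined outcome is the more basic gap, and it decides whether this point applies at all. That is true. Still, the only tests named suit a continuous or ordinal outcome, and Aim 1 measures total testosterone, so a continuous reading is the natural one.

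**Conclusion.** The point holds as one of precision, not validity. Both named tests leave out a baseline value that is already being collected, or on the change reading fix its slope. For a follow-up level, adjusting costs on average about 1.6% of variance (three arms) or 2.4% (two arms) if baseline is uninformative, with 95th percentiles of about 6% and 9%. It breaks even at r of about 0.12 to 0.16, and in the three-arm model lowers variance by about 8% at r = 0.3 and 24% at r = 0.5. Against a t-test on change, ANCOVA is no less precise apart from the same small cost.

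These figures assume equal allocation, about 23 evaluable patients per arm and normal data; every r is an assumption, and no size of gain is claimed. The point lapses if the outcome is the proportion below 50 ng/dL. The visit-count conflict does not affect it, since a baseline and several follow-ups exist under either schedule. The change is worth making because it is cheap, but the trial does not fail without it.

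**What to change.** Replace the t-test sentence with a prespecified ANCOVA of total testosterone, at the visit and on the scale that the investigators name, with arm and baseline testosterone as terms. Report pairwise differences between arms with 95% confidence intervals. Use arm-specific residual variances or robust standard errors, or fit only the two arms being compared, so that a contrast does not depend on equal variances across all three arms. Keep the Wilcoxon test as a sensitivity analysis.

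Optionally, extend this to a mixed model over all follow-up visits with baseline-by-visit terms. It would also use patients who miss the final visit but were seen earlier, whom a single-visit test drops.

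Use the same adjustment for the continuous Aim 2 laboratory outcomes at the visits where each is measured (lipids at 12 and 24 months only). Report the observed baseline correlations for planning the larger trial. Reconcile the visit schedule in Table 2 with the Research Plan and Risks sections before naming the analysis visit.

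The cost is a few sentences, slightly more programming and about 2% of variance on average if baseline proves uninformative. No new visits or samples are needed.

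### Safety laboratory results are compared between arms only by tests of group location, with no count of patients beyond a limit and no interval, so serious elevations in one to three patients per arm would rarely be flagged

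*Combined protocol and SAP*

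**What the plan says.** The Objectives section makes safety and tolerability part of the trial's purpose. Study design says that the secondary outcomes measuring them will "include liver enzymes, thrombogenic, and metabolic factors". Under Risks, the protocol names, among others, "increase risk of venous thromboembolism, diabetes, high blood pressure, coronary heart disease, hepatotoxicity".

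The analysis section (Statistical methods and Data Analysis) is three sentences long:
- Description: "Baseline characteristics and laboratory results will be reported as mean" with SD, "median (interquartile range), or percentages".
- Comparison: "Independent T-test will be used to analyze the difference between treatment groups".
- Fallback: "We may use Wilcoxon rank sum test in case of non-normal distribution".

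The section gives no laboratory limit, worst value per patient, shift from baseline, confidence interval or rule for reading a non-significant result. Percentages are mentioned, but nothing says what percentage would be taken of any laboratory variable, and neither named test compares percentages.

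**The concern.** Some of the named risks are shifts that a whole arm may show. Others, hepatotoxicity above all, show up as a few patients with very abnormal values while the rest of the arm is unchanged. A t-test or rank-sum test asks whether one arm's values sit higher than the other's overall. It does not ask whether more patients in one arm crossed a limit.

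At stake is whether the report can show harm concentrated in one arm. The trial is a pilot meant to inform a larger one, and the designers of that trial will want to know how many patients per arm had a serious elevation and how uncertain that number is. The planned output need not contain either.

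**Working it through.** **Arm size.** The plan targets 70 patients and enrols 80 to allow for 15% dropout. The 80 follows from 70 × 1.15 = 80.5; dividing instead gives 70 / 0.85 = 82.4. The allocation ratio is not stated. With equal allocation to three arms, 70 / 3 = 23.3 per arm; the range is 80 × 0.85 / 3 = 22.7 to 80 / 3 = 26.7. I use 23.

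**Assumptions not in the documents.** Two-sided 0.05; a lognormal liver enzyme with median 20, log-SD 0.4 and upper limit 40; k patients in one arm at five times the limit (200), none in the other.

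**What mean ± SD would show.** Unaffected patients have mean 20 × exp(0.4²/2) = 21.7 and SD 21.7 × √(exp(0.16) − 1) = 9.0. For the affected arm:
- mean m = [200k + 21.7(23 − k)] / 23
- variance s² = [k(200 − m)² + (23 − k)((21.7 − m)² + 9.0²)] / 22
- typical t = (m − 21.7) / √[(s² + 9.0²) / 23], against a critical value of 2.015 on 44 degrees of freedom

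The column for either test comes from simulation under this model (pooled t-test, rank-sum test). The Fisher column is 2 × C(23,k) / C(46,k) for k of 23 versus 0 of 23, capped at 1.

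| k of 23 | Mean ± SD, affected arm (other arm 22 ± 9) | Typical t | Either planned test significant | Fisher p |
|---|---|---|---|---|
| 1 | 29 ± 38 | 0.9 | 5% | 1.00 |
| 2 | 37 ± 52 | 1.4 | 6% | 0.49 |
| 3 | 45 ± 62 | 1.8 | 15% | 0.23 |
| 4 | 53 ± 70 | 2.1 | 71% | 0.11 |

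The typical t explains the pattern. Each extreme value raises the SD along with the mean, and t passes 2.015 only at the fourth patient. The rank test gains little, because it counts 200 and 41 alike as top ranks.

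**What median (IQR) would show.** The median moves by 1 to 2 units. The upper quartile of 23 values lies at about rank 0.75 × 22 + 1 = 17.5, and three extreme patients hold ranks 21 to 23, so their values never enter the summary.

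**Sensitivity.** With an assumed median of 25 and elevations of 3–5 times / 5–10 times the limit, the t-test rejects in 5% / 0.3% of trials for k = 2, 18% / 7% for k = 3 and 53% / 68% for k = 4. The rank test stays between 6% and 13% over the same cases.

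**What counts and intervals would show.** Exact 95% intervals:
- 0 of 23: 0 to 1 − 0.025^(1/23) = 14.8%
- 2 of 23: 1.1% to 28.0%
- 3 of 23: 2.8% to 33.6%

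A count above the plain reference limit carries background. In this model an unaffected patient exceeds 40 when z > ln(40/20) / 0.4 = 1.73, a chance of about 4%, or about one patient in 23. A count beyond a multiple of the limit is therefore needed as well.

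**Shifts in the average.** The 95% half-width for a difference is 2.015 × √(2/23) = 0.59 SD. Power for a true 0.5 SD difference is 38% (37% to 42% at 22 to 26 per arm), so a non-significant result leaves sizeable differences open.

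**The case against.** The strongest reply has five parts.

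- **The plan is not confined to averages.** It allows mean ± SD, median (IQR) and percentages, with a rank test as fallback. This stands. At 3 of 23, mean ± SD would read about 45 ± 62 against 22 ± 9, which an alert reader would notice. But median (IQR) is equally allowed, is the natural choice for skewed enzymes, and would hide it.
- **Location tests fit much of what is hypothesised.** Hypothesis 2a predicts a rise in thrombogenic factors and changes in metabolic factors, and the Risks section also names lipoprotein and triglyceride changes. This stands, so the tests should be kept and the threshold argument confined to analytes with a clinical limit.
- **The insensitivity is bounded.** With 4 of 23 affected, detection rises to about 71%. This stands; the point concerns one to three patients.
- **Counts bring no significance.** Fisher's test is also non-significant for 2, 3 or 4 of 23 versus 0. This stands. The gain is visibility and an honest interval.
- **Patients are watched.** The Research Plan has a hematologist review results and advise the treatment team. This stands for patient care, but nothing turns that review into an outcome reported by arm.

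A reader might also infer that a non-significant test will be reported as showing the regimens equally safe. No passage says so, and naming a t-test does not rule out giving the difference with its interval. All that can be said is that nothing in the plan guards against that reading.

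**Conclusion.** The point holds as a gap in by-arm analysis and reporting. For analytes where harm means a few patients beyond a limit, the planned tests are significant in about 6% of trials with 2 of 23 affected and about 15% with 3 of 23, against a nominal 5%. The planned summaries may or may not reveal the cases, depending on which is chosen.

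The size rests on assumptions: equal allocation, two-sided 0.05, and an enzyme distribution and limit that the documents do not supply. The sensitivity runs give the same picture for one to three patients.

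Two stronger readings are not supported. The plan does not leave serious elevations clinically undetected, given the hematologist review. Nor are its tests wrong for every safety analyte, since they answer the hypothesised shifts. This is a worthwhile, cheap improvement and does not call for a larger sample in a pilot.

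**What to change.** In Statistical methods and Data Analysis:

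1. Keep the location comparisons and report each between-arm difference with a 95% confidence interval.
2. For Table 2 analytes with a clinical reference limit, such as liver tests and electrolytes, report by arm the number and percentage of patients with any post-baseline value beyond the laboratory reference limit, and beyond a multiple of it fixed before analysis, with exact 95% confidence intervals.
3. For the same analytes, give each patient's worst post-baseline value and shift from baseline, including unscheduled samples. Show the number of samples per patient by arm, because more sampling gives more chances to cross a limit.
4. Present the counts descriptively, without a further significance test.
5. State that a non-significant test is not evidence of similar safety, and that any safety statement is limited by the intervals.

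These are reporting thresholds only and change no clinical management. The scheduled data are already in Table 2, so the cost is a few tables and sentences. The downside is wide intervals (even 0 of 23 leaves an upper limit of 14.8%) and a more modest safety statement.

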Study Protocol Cover page

Title: Effectiveness, safety, and tolerability of different estradiol dosing regimens in transgender females.

NCT Number: NCT05010707

Date: May 26, 2022

Washington University in St. Louis

Version Date: May 26th, 2022

Principal Investigator: [name]

Study Title: Effectiveness, safety, and tolerability of different estradiol dosing regimens in transgender females.

Faculty Sponsor: [name]

- **Objectives**

The purpose of this open label, pilot, randomized clinical trial is to evaluate the effectiveness, safety and tolerability of estrogen use in transgender female and the degree of testosterone suppression achieved in this population when placed on sublingual 17-beta estradiol in comparison to transdermal 17-beta estradiol for gender affirming pharmacological therapy over the first two-years of treatment.

This study is important because, to our knowledge, this is the first randomized clinical trial evaluating the effectiveness, safety, and tolerability of estrogen in transgender female. There are no previous data comparing the different presentation of estrogen options in transgender women; therefore, this clinical trial will determine the best strategies and methods required to develop a larger randomized clinical trial. This study will also provide information useful to close the medical knowledge gap to provide safe and competent care to transgender female patients.

Aims

Aim 1. In this randomized clinical trial, we will evaluate the degree of testosterone suppression by measuring total testosterone level in transgender female patients undergoing hormonal affirming therapy randomized to sublingual 17 beta estradiol or transdermal 17 beta estradiol, in conjunction with spironolactone (antiandrogen), for a period of 2 years.

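### The plan names no primary visit and no rule for patients who leave; its two-sample tests, applied at month 24, would leave out about 10 to 12 of 80 patients and their earlier testosterone values

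*Combined protocol and SAP*

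**What the plan says.** Under Study design the plan states "Primary outcome is degree of testosterone suppression". Aim 1 adds that "we will evaluate the degree of testosterone suppression by measuring total testosterone level in transgender female patients", over a period of two years. Neither place gives a visit, a change from baseline or a responder definition.

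Under Subjects the plan first states "We aim to enroll a total of 70 patients", and then "To account for 15% of potential dropout, we have planned to enroll a total of 80 patients". That is all it says about dropout.

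The section on statistical methods and data analysis consists of descriptive summaries, the sentence "Independent T-test will be used to analyze the difference between treatment groups", and an optional Wilcoxon rank sum test for non-normal data. It has no analysis population, missing-data rule, repeated-measures model or sensitivity analysis.

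Table 2 has a row "Hormone levels", marked at baseline and at months 6, 12, 18 and 24. The Research Plan also has hormone levels checked about every 4 weeks until estradiol is within goal.

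**The concern.** A two-sample t-test or rank sum test takes one value per patient. If that value is month-24 testosterone, a patient without it contributes nothing, even when values at months 6, 12 and 18 are on file.

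Extra enrolment restores the number of patients but does not restore the randomised comparison. Suppose poorly suppressed patients leave one regimen more often than another. Those who stay on it then look better suppressed than the group that was randomised to it. Such a pattern is possible here, because treatment is open label and the arms differ in route and in number of daily administrations. The results are meant to shape a larger trial, so a distorted contrast would be carried into its design.

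Because neither the visit nor the handling of leavers is fixed, several analyses fit the text: month-24 completers, last available value, month 6, or each visit in turn. The choice could be made after the data are seen.

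**Working it through.** **1. Dropout allowance (Subjects).**
- Multiplying: 70 × 1.15 = 80.5, which reproduces the plan's 80.
- Dividing: 70 / (1 − 0.15) = 82.4, or 83, which does not.
- Loss at the stated rate: 0.15 × 80 = 12, leaving 68.
- Loss implied by the target: 80 − 70 = 10, or 12.5%.
- The supportable range is therefore 10 to 12 patients.

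**2. Loss of precision.** Assumed: 1:1:1 allocation (the ratio is not stated), two-sided alpha 0.05, 80% power.
- Pairwise detectable difference in SD units = (1.960 + 0.842) × √(2/n).
- 80 patients, n = 26.7 per arm: 0.77 SD.
- 68 patients, n = 22.7 per arm: 0.83 SD.
- The standard error rises by √(80/68) = 1.085, about 8%. Part of this is unavoidable under any analysis. With purely random dropout, the variance of the completer t-test is 3% to 13% larger than that of a model using all visits.

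**3. Possible bias.** The documents give no SD, correlation or dropout pattern, so all of these are assumptions. The simulation has two arms of 27, no true difference, four post-baseline visits and an SD of 0.8 log units. Patients leave after visit 1, 2 or 3. In one arm the chance of leaving rises with the last standardised value z, with weight exp(2z). In the other arm leaving is random. A negative bias makes the arm with selective loss look better suppressed.

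| Dropout, the two arms | Correlation | Completer bias (log units) | False ratio | Completer type I error |
|---|---|---|---|---|
| 15% and 15% | 0.4 | -0.07 | 0.93 | 6% |
| 15% and 15% | 0.6 | -0.10 | 0.90 | 8% |
| 15% and 15% | 0.8 | -0.14 | 0.87 | 10% |
| 22% (selective) and 8% | 0.6 | -0.16 | 0.85 | 11% |

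With 23 completers per arm the standard error is 0.8 × √(2/23) = 0.236. The three equal-dropout biases (0.071, 0.103 and 0.135 before rounding) are thus 0.30, 0.44 and 0.57 of a standard error.

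- With weaker one-sided selection, exp(z), the bias starts at about -0.05 and type I error is 6% to 7%.
- With the same selection in both arms the bias is about 0. With random loss the t-test is unbiased.
- A repeated-measures model, with its covariance estimated from the 27 per arm, has bias of about 0 and type I error of 4% to 7% under the one-sided scenarios.

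**The case against.** **The plan does not say that dropouts are excluded.** A reader might infer that the plan discards patients who leave and ignores their earlier testosterone. The documents do not support that. They fix no primary visit and are silent on missing values, so a per-visit, month-6 or last-value comparison would fit the text equally well. This stands. The omission is a consequence of applying the named tests at month 24, not a stated rule.

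**The rate is only potential.** The plan calls the 15% potential dropout, and its own target implies 12.5%. This stands too, hence the range of 10 to 12. Nor do the documents set a dropout level above which the result would be unacceptable.

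**The bias scenario is chosen.** A weight of exp(2z) multiplies the tendency to leave about 7.4-fold per SD, and it acts in one arm only. At exp(0.5z) the bias is only -0.03 to -0.05, with type I error of 5% to 6%. Titration toward a testosterone target could also narrow both the spread and the selection. These limits are fair. The figures show what could happen, not what is expected.

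**The model is favoured by construction.** In the simulation, leaving depends only on observed values and never precedes the first visit. That stands as a limitation. An objection that the model needs a known covariance does not, since the result holds with the covariance estimated at this sample size.

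**It is a pilot without stated alpha or power.** This lowers the weight of a modest type I error. It does not remove the need to define the primary comparison, because the results are to guide a larger trial.

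**Counting leavers as not suppressed.** It is tempting to score patients without a month-24 value as failures on testosterone below 50 ng/dL. That threshold is a titration target in the dosing guidelines, not a stated outcome, and the scoring can itself create bias. If 75% are truly suppressed in both arms (assumed) and dropout is random at 22% and 8%, the scored shares are 0.75 × 0.78 = 58.5% and 0.75 × 0.92 = 69.0%. That is a false difference of about 11 percentage points, in a setting where the completer t-test is unbiased.

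**Conclusion.** The concern holds in a limited form. The plan names neither the primary visit nor a rule for patients without a value there, and its only between-group methods use one value per patient. Applied at month 24, they would leave out 10 to 12 of 80 patients and make no use of testosterone already collected.

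The certain cost is a small loss of precision. The possible cost is bias of about -0.05 to -0.16 log units with type I error of 6% to 11%. That range rests on an assumed SD of 0.8 log units, a correlation of 0.4 to 0.8, and moderate to strong selective loss in one arm only. If loss is random or alike across arms, the bias is about 0. A better analysis is available from visits already scheduled, so the change should be made, although nothing in the documents shows that the result will be biased.

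**What to change.** In the section on statistical methods and data analysis:

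- Name month 24 as the primary visit.
- Make the primary analysis a likelihood-based repeated-measures model of log total testosterone at months 6, 12, 18 and 24, with baseline testosterone as a covariate. Analyse by assigned arm and include every randomised patient with any post-baseline value.
- Report the pairwise month-24 contrasts among the three arms.
- Add one sensitivity analysis that shifts the unobserved values of dropouts upward.
- Report dropout by arm, with the reason and the last testosterone value.
- Keep the completer t-test as a supporting analysis.

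The cost is revised wording and slightly more analysis work, with no new visits, tests or patients. The downsides are small. The model assumes that leaving depends on observed values, which is why the sensitivity analysis is needed, and patients who leave before month 6 still add little.
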